Specific Aim 2: Determine the safety of insulin glargine 0.4 unit/kg early administration within four hours from IV Insulin infusion initiation.

III. METHODS

A. Study Design and Methodology:

This will be a prospective, open-label, intervention cohort study including all consecutive adult patients with Diabetes Ketoacidosis (DKA) getting admitted to Fairview Hospital-Medical Intensive Care Unit (FV-MICU). Screening of patient eligibility and informed consent will be done by the MICU admitting physician once the patient gets admitted to MICU. Participants will be given an overview of the study, including study procedures, and potential risks. Participants will be given adequate time to review the consent form and have opportunities to ask questions. After the informed consent process has been completed and a consent form has been signed, a copy of the consent will be provided to the participant and another copy will be secured in the Principle Investigator office in a locked cabinet. Enrolled participants in the intervention group will receive an Insulin Glargine 0.4 Unit/kg within 4 hours from initiating the IV Insulin Infusion, as per the Cleveland Clinic DKA protocol. The remaining of the management will be following the CC DKA protocol including continuing IVII till Anion Gap Closure ($AG \leq 12$), Basal Metabolic Panel Q 2 hrs, and replacing electrolytes as indicated. After closing the anion gap, the decision for giving more Basal Insulin doses will be left to the treating physician's discretion. For patient safety, Point Of Care (POC) blood glucose will be checked hourly before IVII discontinuation. After IVII discontinuation, the BG will be checked with meals, bedtime and 2 am if the patient maintain good oral intake, if not, the BG will be checked q 4 hrs. Target BG 150 – 200 mg/dl during the DKA management and 140 – 180 mg/dl after DKA resolution as per American Diabetes Association recommendations. In case of any hypoglycemia event, this goal will be achieved by using Dextrose containing fluid or carbohydrate enriched oral intake which will be left to the treating physician discretion depending on patient awareness and severity of hypoglycemia. Also, the pre meals and correctional insulin doses after AG closure will be left to the treating physician's discretion. After AG closure the pre meals and correctional insulin doses will be left to the treating physician's discretion. In case of not closing the AG after 24 hours from the initial Glargine dose, the decision for further Glargine doses will be left to the treating physician's discretion.

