
The investigator team will be notified by the MICU attending after each participant enrollment, so one of the team members will present to MICU to collect the data prospectively in a standardized Data Collecting Sheet (DCS) by using REDCap and all protected health information (PHI) will be de-identified. As regards the control group, an E-research request will be submitted to provide a list by

all the consecutive adult patients admitted to FV-MICU with a diagnosis of DKA in the period between January 1st 2019 till the date of IRB approval. Prespecified sample size and matched in basal patient characteristics and DKA severity will be selected as the control group. Data will be collected retrospectively for the control group and will be recorded directly into the DCS in RedCap. Clinical outcomes will be compared between the intervention and control groups. The primary outcome includes time to anion gap closure ($AG \leq 12$). Secondary outcomes include hospital Length Of Stay (LOS), ICU LOS, total IVII dose, the incidence of transitional failure (defined recurrence of DKA after initial IVII discontinuation within 24 hours and requiring reinitiating the IVII), the incidence of hyperglycemia (> 180 mg/dL) and hypoglycemia (defined as ≤ 70 mg/dL, <54 , <40) during 24 hours from Insulin Glargine administration.

B. Definition of main exposures and outcomes:

Diagnosis of DKA will be made by ICD-10-CM code E10.10, E11.10, or meeting the ADA definition; $BG \geq 250$ mg/dl, $AG > 12$, and positive Ketones in serum or urine

DKA classification as the following table from ADA:

	Mild (plasma glucose >250 mg/dl)	Moderate (plasma glucose >250 mg/dl)	Severe (plasma glucose >250 mg/dl)
Arterial pH	7.25–7.30	7.00 to <7.24	<7.00
Serum bicarbonate (mEq/l)	15–18	10 to <15	<10

For the hyperglycemia analysis, patients will be compared in the following categories according to their mean or median (depending on the normality of the data distribution) blood glucose throughout the hospital stay:

- Mean/median BG <80 mg/dL
- Mean/median BG 81-100 mg/dL
- Mean/median BG 101-140 mg/dL
- Mean/median BG 141-180 mg/dL
- Mean/median BG > 180 mg/dL'
- Mean/median BG > 240 mg/dL

Hypoglycemia will be defined by three categories:

- any glucose level below 70 mg/dL
- any glucose level less than 54 mg/dL
- any glucose level less than 40 mg/dL

For Time of Anion Gap Closure (TAGC) will use the ADA definition: $AG \leq 12$ mEq/L

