Transitional failure will be defined as the recurrence of DKA ($BG \geq 250$ mg/dl, $AG > 12$, and positive Ketones in serum or urine) after initial IVII discontinuation within 24 hours and requiring reinitiating the IVII.

C. Study Population

Intervention vs Control group

- Intervention group: All consecutive adult patients getting admitted to FV- MICU and meet the inclusion criteria and accepted to receive insulin glargine early as per the protocol. They will receive insulin glargine 0.4 unit/kg within 4 hours from initiating the IV Insulin Infusion, as per the Cleveland Clinic DKA protocol.
- Control group: prespecified and matched sample size, consecutive adults who admitted to FV-MICU with a diagnosis of DKA in the period between January 1st 2019 till the IRB approval date and didn't receive basal insulin before AG closure.

Inclusion criteria:

- Age \geq 18 years old
- Meet DKA definition as above
- Having the capacity to sign Informed consent

Exclusion Criteria

- IV insulin infusion initiated more than 4 hours.
- Persistent hypotension (SBP<80 mmHg despite receiving 1000cc normal saline).
- Require Vasopressor
- Acute Coronary Syndrome
- Pregnant
- End-stage renal disease
- Unwilling to consent to participate in the trial
- Currently under police custody
- Transferred from another hospital
- Require emergent surgery
- Alcoholic Ketoacidosis

Study Variables:

General Informations:

- Patient name
- MRN
- Age
- Sex (Male, Female, Others)
- Race (White, Black, Asian, Other)
- Ethnicity (Hispanic vs. Non-Hispanic)
- Weight on admission (kg)
- BMI (Kg/m²)
- Height (cm)
- Date of Hospital admission
- Date of ICU admission

- Date of DKA diagnosis (MM/DD/YY)
- Precipitating cause of DKA
 - Noncompliance
 - New-onset
 - Infection
 - Cerebrovascular accident
 - alcohol abuse
 - pancreatitis
 - Drugs
 - Others

Past Medical history

- Type of diabetes:
 - Type 1 DM
 - Type 2 DM
 - Cystic fibrosis-related diabetes
 - Steroid-induced diabetes
 - Other or no clear diagnosis
- Known diagnosis of other major medical comorbidities (CAD, CHF, HTN, COPD, asthma, liver disease, CKD, cancer, other)
- On Renal Replacement Therapy (Y/N)
- Using Basal insulin at home (Yes/No/ unknown)
- If previous point answer is yes check the corresponding insulin type and write the dose: (Glargine, Detemir, Degludec, NPH, Continuous Insulin Pump) (dose: IU)
- Home total basal insulin dose (units)

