- Non-insulin antihyperglycemics taken at home prior to admission, including the type
 - Sulfonylureas
 - Thiazolidinediones
 - Dipeptidyl peptidase-4 (DPP-4) inhibitors
 - Biguanides
 - Glucagon like peptide-1 (GLP-1) analogues
 - Sodium-glucose transport protein 2 (SGLT2) inhibitors
 - Meglitinides
 - Alpha glucosidase inhibitors
 - Amylin analogues
- History of immunosuppression (history of cancer, HIV or auto-immune disease or organ transplant, chronic steroid)

Initial Laboratory values:

- Anion gap (mEq/L)
- Bicarbonate (mEq/L)
- Glucose (mg/dL)
- Beta-Hydroxybutyrate (mmol/L)
- Ketones in the urine (Y/N/Unknown)
- HbA1c %
- Lactate (mmol/L)

Intervention and outcomes:

- IV insulin infusion starting time
- Insulin glargine administration time
- Anion Gap closure time
- IV insulin discontinuation time
- Number of hours of IVII
- Total IV insulin infusion has been given
- Total IV insulin/weight
- Total IV fluid during DKA management
- Date of discharge from ICU
- Date of discharge from hospital
- Hospital Length Of Stay (days)
- ICU LOS (hours)
- Transitional failure (recurrence of DKA)?

Hypoglycemia Events

- Hypoglycemia event within 24 hrs from glargine
- Time of the hypoglycemia
- How many hours after the glargine administration?
- Severity
- How it has been treated

Hyperglycemia Events

- Hyperglycemia Event after IVII discontinuation by 24 hours (Y/N)
- time of the hyperglycemia event
- Severity of hyperglycemia
- How many hours after IVII discontinuation

D. Outcomes

Primary outcome: Time to anion gap closure (hours).

Secondary outcomes:

- Hospital Length of stay (days)
- ICU length of stay (hours)
- Total IV insulin infusion dose (International unit)
- Incidence of transitional failure (percentage).
- Incidence of hyperglycemia (> 180 mg/dL) during 24 hours from Insulin Glargine administration (percentage).
- Incidence of hypoglycemia (defined as ≤ 70 mg/dL, <54, <40) during 24 hours from Insulin Glargine administration (percentage).

IV. DATA COLLECTION

For the control group, the data will be collected retrospectively and recorded in standardized DCS in RedCap. For the intervention group, the data will be collected prospectively by the investigator team members and observations will be recorded in standardized DCS in RedCap. All protected health information (PHI) will be de-identified for both intervention and control group by using de-identification function in REDCap.

V. DATA ANALYSIS

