For patient safety, insulin therapy is carrying a risk of hypoglycemia events. Previous studies didn't show any additional risk when insulin glargine has been given before anion gap closure comparing to the common practice, after anion gap closure. Shankar and Hsia's studies (4, 8) didn't reveal any hypoglycemic events between both groups. Both Doshi and Houshyar's studies (6, 7) revealed similar hypoglycemic events between both intervention and control groups and were neither clinically nor statistically significant.

The possible explanation for that is although the overlap time of glargine and IV insulin infusion is longer in the intervention group, the insulin infusion rate is getting adjusted hourly to meet the body requirement to decrease the blood sugar by a range of 50 - 100 mg/dl per hour. To ensure patient safety, CCF Hypoglycemia protocol is getting followed in all patients receiving insulin including our enrolled participants. Before IV insulin discontinuation, the blood glucose level is getting checked hourly as per protocol. Once the AG is closed and insulin infusion is discontinued, the patient who is maintaining oral intake, blood glucose will be checked with meals, bedtime, and 2 am. If the patient having poor oral intake, blood glucose will be checked q 4 hours. Different treatment options for any hypoglycemic events are available in the protocol depending on the severity of the hypoglycemia event and patient awareness, ranging from oral carbohydrate supplement to IV fluid containing dextrose. After AG closure the pre meals and correctional insulin doses will be left to the treating physician's discretion.

For data safety, all data will remain anonymous, and no personal health information will be associated with any data resulting from this study. Data will recorded directly into a secure REDCap database. No PHI will be saved on non-HIPAA protected devices. All protected health information (PHI) will be de-identified by using RedCap.

All subjects will be provided a consent form describing this study and with sufficient information to make an informed decision about participation in the study. The consent form will be submitted with the protocol for review and approval by the IRB. The formal consent of a subject, using the IRB-

approved consent form, will be obtained before the subject undergoes any study procedure. This consent form must be signed by the subject, and the investigator-designated research staff obtaining the consent.

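### The >180 mg/dL hyperglycemia outcome can score on-target infusion readings as events, mainly in the intervention group, and conflicts with two other definitions in the plan

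*Combined protocol and SAP*

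**What the plan says.** **Outcome.** Section III.D (and the end of III.A) lists "Incidence of hyperglycemia (> 180 mg/dL) during 24 hours from Insulin Glargine administration (percentage". No expected rate is given, and the number of readings that makes an event is not stated.

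**Glucose targets.** Section III.A: "Target BG 150 – 200 mg/dl during the DKA management and 140 – 180 mg/dl after DKA resolution". The infusion is managed by "continuing IVII till Anion Gap Closure", with glucose checked hourly while it runs. Afterwards checks are at meals, bedtime and 2 am, or every 4 h if intake is poor.

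**Where the window starts.** Section III.C on the intervention group: "They will receive insulin glargine 0.4 unit/kg within 4 hours from initiating the IV Insulin Infusion". Controls are patients who "didn't receive basal insulin before AG closure".

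**Other hyperglycemia definitions.** Section III.B compares patients by categories of mean or median glucose over the whole hospital stay. The variable list in III.C records a yes/no hyperglycemia event within 24 h after the infusion is stopped, with its time and severity. That field carries no threshold.

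**The concern.** A reading of 181–200 mg/dL during the infusion meets the plan's target and also exceeds the outcome's threshold. The outcome would then partly measure how long a patient was on infusion inside the window, not whether glucose control failed.

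The two groups are also scored in different phases. A window anchored on glargine takes in infusion time for intervention patients. For controls it starts after closure, when the upper target limit equals the threshold and readings are fewer. A control who received no glargine has no defined window. Both features push the count up in the intervention group whatever glargine does. The Background cites less rebound hyperglycemia in the 24 h after DKA resolution (35% v 51%) among the encouraging results of one earlier randomized trial. The listed outcome does not measure that quantity.

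**Working it through.** **1. The plan's own figures.** There is no planned hyperglycemia rate to reproduce. The sample size in Section V can be reproduced, and this confirms the closure time used below. The difference is 0.20 × 15.6 = 3.12 h and the SD is 6 h. With one-sided α 0.025 and power 0.90, n per group = 2 × (1.960 + 1.282)² × 6² / 3.12² ≈ 78, or 156 in total against the stated 160. Expected mean closure on early glargine is therefore 15.6 − 3.12 = 12.48 h.

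**2. Threshold against target.** 180 lies within 150–200. The part of the band above it is (200 − 180)/(200 − 150) = 0.40.

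**3. Infusion time inside the window.** With glargine at the 4 h limit, the mean overlap is 12.48 − 4 ≈ 8.5 h; earlier dosing lengthens it. If closure stays at 15.6 h, it is 15.6 − 4 = 11.6 h. These are means. With closure roughly normal (assumption), (12 − 12.48)/6 = −0.08, so about 47% of patients close before 12 h and have less than 8 h of overlap.

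**4. Entry glucose.** Section VIII says the infusion is adjusted "to decrease the blood sugar by a range of 50 - 100 mg/dl per hour". From 250 mg/dL, 180 is reached in 70/100 = 0.7 h to 70/50 = 1.4 h. A patient dosed at 4 h is still above 180 only if glucose started above 180 + 4 × 50 = 380 (slow fall) or 180 + 4 × 100 = 580 (fast fall).

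**5. Chance of at least one on-infusion reading above 180.** This assumes that one reading is enough.

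| Assumption for on-target readings | Readings | Result |
|---|---|---|
| Independent, spread evenly over 150–200 | 8 | 1 − 0.6⁸ = 98% |
| Independent, 20% exceed 180 | 8 | 1 − 0.8⁸ = 83% |
| Independent, 10% exceed 180 | 8 | 1 − 0.9⁸ = 57% |
| Centered at 175, SD 12.5, hourly correlation 0.8 (simulated) | 11 | 80% |
| Centered at 175, SD 7, hourly correlation 0.9 (simulated) | 11 | 55% |

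**6. Combined simulation.** Assumptions: median entry glucose 300–500 mg/dL with a floor of 250; glargine between 1 and 4 h; fall of 50–100 mg/dL per hour; closure mean 12.48 h, SD 6 h; SD of readings 7 or 12.5. Hourly correlation was 0 to 0.9 for readings centered at 175, and 0.8 or 0.9 for those centered at 165. The share scored was about 48–97% at 175 and about 12–84% at 165. Only the infusion part of the window is counted, so later readings can only add events.

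**7. Unequal phases with no treatment effect.** Take 8 hourly infusion readings plus (24 − 8.5)/4 ≈ 4 later ones, 12 in all, for an intervention patient, and 24/4 = 6 for a control. Give every reading the same independent chance of exceeding 180 (assumption).
- Chance 20%: 1 − 0.8¹² = 93% v 1 − 0.8⁶ = 74%.
- Chance 10%: 1 − 0.9¹² = 72% v 1 − 0.9⁶ = 47%.

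These gaps come from the number of readings alone. The lower target after closure is not included.

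**The case against.** A reader might infer that nearly every early-glargine patient must have the event, so that the outcome sits near 100%. The documents do not support that. It needs a rule that a single reading counts, and the plan says this only for hypoglycemia. It needs evenly spread, independent readings, which is unlikely for hourly values under titration. It treats a mean closure time as a minimum. The entry glucose does not secure it either: step 4 shows that glucose can be below 180 before a 4 h dose, no distribution of starting glucose is given, and a diagnosis code alone also qualifies: "Diagnosis of DKA will be made by ICD-10-CM code E10.10, E11.10, or meeting the ADA definition; $BG \geq 250$ mg/dl".

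On the mean/median rule of Section III.B, on-target readings of 181–200 do not by themselves put a patient above 180: an even spread over 150–200 averages 175. And the variable list already records the event after the infusion stops, so the data as collected may not follow the listed outcome.

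These points remove any fixed rate, but they do not rescue the definition. A yes/no event reported as an incidence most naturally means any reading. The existence of two other definitions shows that the plan has not settled which one Section III.D means. It is also fair that starting both windows at infusion start would remove the imbalance between groups; on-target readings would then still score, but in both. Finally, this is one of six secondary outcomes and has no part in the sample size.

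**Conclusion.** The point holds as a conflict of definition with a possible bias against the intervention. On the documents' own figures, the threshold lies inside the target during DKA management, and the intervention window includes on average about 8.5 h or more of infusion time. Control windows fall after closure, mostly under the 140–180 target and with fewer checks.

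The size is uncertain. Under the any-reading rule, the share of intervention patients scored could run from a minority to nearly all, about 12–97% across the assumptions tried. The 93% v 74% and 72% v 47% comparisons illustrate direction only; they rest on independent readings and a common chance per reading. If the rate did prove close to the ceiling, the outcome would discriminate poorly: with 80 per group (an equal split, which the plan does not state) and one-sided α 0.025, power is 0.18 for 98% v 95%. The plan should be changed here, but neither the primary outcome nor the sample size is affected.

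**What to change.** Define the hyperglycemia outcome in both groups as any reading above 180 mg/dL in the 24 h after the IV insulin infusion is discontinued. Use the same wording in Sections III.A and III.D, and add the threshold to the existing data-sheet field. Label the mean/median categories in III.B as a separate descriptive analysis over the hospital stay. If on-infusion readings are kept, report them separately, against the target the plan states for that phase.

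This places both groups in the same phase, matches the threshold to the post-resolution target, and comes closer to the rebound result cited in the Background.

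The cost is wording. The infusion stop time and the post-infusion event are already on the data sheet. The downside is that fewer readings are scored and early glucose no longer contributes to this outcome. No glucose target or treatment rule changes.

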Early administration of basal insulin has seldom been studied in DKA management. In 2012, Hsia et al (4) conducted a prospective randomized controlled trial involving 61 hospitalized adults with known diabetes and presented by hyperglycemia who were randomized to receive treatment with IV insulin infusion (IVII) with or without glargine (0.25 Unit/kg). The primary outcome of rebound hyperglycemia was reduced with early administration of glargine (33.3% vs 93.5%, $P < 0.001$) without increasing the risk of hypoglycemia (none in the intervention group vs three cases in the control group). Accordingly, in 2013, the Joint British Diabetes Societies updated their guideline on DKA management in adults to advise early administration of home basal insulin dose (5). After that, two randomized controlled trials were published in 2015, both with a sample size of 40 patients, investigated initiating Insulin Glargine within 2-3 hrs from IVII initiation compared to IVII alone, using a dose of 0.3 unit/kg (6) and 0.4 unit/kg (7). Although both the studies did not demonstrate statistical significance in the primary and secondary outcomes, it could be argued they were clinically significant. For examples, time to AG closure 13 +/- 6 vs 16 +/- 6 hours, IVII dosage 84 ±45 U vs 116 ± 91 U, rebound hyperglycemia for 24 hours after DKA resolution 35% vs 51%, hospital LOS 5.1 vs 5.9 days (intervention and control groups respectively) (7) and no difference in hypoglycemia events between both groups in both studies.

The limitations in the previous studies such as being underpowered, flaws in reporting data, and lacking a unified management protocol make it difficult to state a definitive evidence-based recommendation for using basal insulin early in DKA in adults. For that reason, we propose prospective, open-label, intervention cohort study to test our hypothesis that an insulin glargine dose of 0.4 Units/kg early administered (within four hours) of IVII initiation in DKA management in adult would be effective and safe in shortening the time to anion gap closure comparing to the standard practice.

II. STUDY OBJECTIVE(S): INCLUDING SPECIFIC AIMS AND/OR HYPOTHESES

Specific Aim 1: Test the hypothesis that early Glargine 0.4 unit/kg administration within 4 hours from IV insulin initiation will provide faster anion gap closure in Diabetic Ketoacidosis management in MICU, at least 20% than late administration.

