The sample size calculation considered the average time of AG closure in the last 3 months in FV-MICU was 15.6 ± 2.5 hours (CI 95%) and SD of 6 hours. Using one-sided α of 0.025 and an β of 0.10, an expected 20% difference between the two groups, a sample size of 160 totally of the participant will be adequate.

Categorical variables will be described as frequency rates and percentages, and continuous variables will be described using mean, median, and interquartile range (IQR). Proportions for categorical variables will be compared by Chi-squared test of Fisher's exact test. Means for continuous variables will be compared by Student's t-test if normally distributed and Mann-Whitney test if not normally distributed. All statistical analyses will be performed with a one-sided p-value < 0.025 to determine statistical significance. All statistical analyses will be completed by study investigators using Statistical Analysis Software (SAS).

VI. DATA AND SAFETY MONITORING PLAN (if applicable)

All data will be stored in a secured REDcap database. No PHI will be saved on non-HIPAA protected devices. All protected health information (PHI) will be de-identified by using RedCap.

To ensure patient safety, CCF Hypoglycemia protocol is getting followed in all patients receiving insulin including our enrolled participants. Before IV insulin discontinuation, the blood glucose level is getting checked hourly as per protocol. Once the AG is closed and insulin infusion is discontinued, the patient who is maintaining oral intake, blood glucose will be checked with meals, bedtime, and 2 am. If the patient having poor oral intake, blood glucose will be checked q 4 hours. Different treatment options for any hypoglycemic events are available in the protocol depending on the severity of the hypoglycemia event and patient awareness, ranging from oral carbohydrate supplement to IV fluid containing dextrose.

VII. STUDY LIMITATIONS

- Retrospective EPIC data review for the control group. Single-center.

VIII. ETHICAL CONSIDERATIONS

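### Every planned hyperglycemia comparison cuts continuous glucose into categories and none uses the glucose scale; this discards information, by an amount the documents cannot fix

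*Combined protocol and SAP*

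**What the plan says.** III.D (Outcomes) lists as a secondary outcome "Incidence of hyperglycemia (> 180 mg/dL) during 24 hours from Insulin Glargine administration (percentage"; III.A says the same. III.B (Definition of main exposures and outcomes) adds a hyperglycemia analysis in which each patient's mean or median glucose over the hospital stay is placed in one of six bands, from below 80 to above 240 mg/dL.

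The data sheet in III.C (Study Variables) has "Hyperglycemia Event after IVII discontinuation by 24 hours (Y/N", plus fields for the time of the event, its severity and the hours since the infusion stopped. It does not say that severity is a glucose value, and no outcome or test uses that field.

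For testing, section V (Data Analysis) says: "Proportions for categorical variables will be compared by Chi-squared test of Fisher's exact test". It gives continuous variables a general t-test or Mann-Whitney rule, but no post-baseline glucose measure is named for it. The significance rule is common to all outcomes: "All statistical analyses will be performed with a one-sided p-value < 0.025 to determine statistical significance".

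Glucose is measured often. III.A and VI describe hourly checks during the infusion, then checks with meals, at bedtime and at 2 am, or every 4 hours if oral intake is poor.

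**The concern.** A patient whose glucose reaches 185 mg/dL and one who reaches 400 mg/dL count the same under the >180 rule, while 178 and 185 count as opposites. The bands lose less, but they still discard differences within a band. Treated as categories, they fall under the chi-squared/Fisher rule. III.B derives a continuous value per patient and then gives up its scale before the groups are compared, and the plan offers no reason for doing so.

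The 140–180 mg/dL range in III.A is a treatment target after DKA resolution. It explains why 180 is a readable cut-point, but not why the test must be binary.

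What is at stake is precision on one secondary outcome. The background section cites less rebound hyperglycemia among the possible benefits of early glargine and criticises earlier studies as underpowered. A comparison that discards information makes it more likely that a real glucose difference is reported as none.

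**Working it through.** **1. The plan's own figure.** Section V gives "the average time of AG closure in the last 3 months in FV-MICU was 15.6 ± 2.5 hours (CI 95%) and SD of 6 hours" and "Using one-sided α of 0.025 and an β of 0.10, an expected 20% difference between the two groups", and concludes that "a sample size of 160 totally of the participant will be adequate". A 20% difference is 0.20 × 15.6 = 3.12 h. Then n per group = 2 × (1.960 + 1.282)² × 6² / 3.12² = 77.7, so 78 per group and 156 in total (158 with a t-based calculation). The stated 160 is reproduced, and 80 per group gives 90.8% power. This concerns anion gap closure only; the plan states no power for hyperglycemia.

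**2. Inputs for an illustration.**
- 80 per group: 160 total, with 1:1 allocation assumed because no ratio is stated.
- One-sided 0.025, from section V.
- Rates from the background section: "rebound hyperglycemia for 24 hours after DKA resolution 35% vs 51" (percent, intervention vs control), read for now as the share of patients with an event.
- A single cut on an underlying glucose scale with equal spread in both groups. This is an assumption; the documents give no glucose SD.

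**3. Yes/no test at 35% vs 51%.** The pooled rate is 0.43.
- Null SE = √(2 × 0.43 × 0.57 / 80) = 0.0783.
- Alternative SE = √((0.35 × 0.65 + 0.51 × 0.49) / 80) = 0.0772.
- Power = Φ((0.16 − 1.96 × 0.0783) / 0.0772) = Φ(0.085) = 53%.
- Fisher's exact test, by simulation (5,000 runs): about 47%.

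**4. The same effect uncut.**
- Normal scale: d = 0.025 − (−0.385) = 0.410. The t-test has power Φ(0.410 × √40 − 1.96) = 74%. Mann-Whitney (relative efficiency 0.955) has Φ(0.410 × √(40 × 0.955) − 1.96) = 72%.
- Log-normal scale (log SD 0.5 assumed), by simulation: t-test 68%, Mann-Whitney 71%.
- Logistic scale: log-odds difference 0.659, divided by π/√3 = 1.814, gives d = 0.363. The t-test has power Φ(0.363 × √40 − 1.96) = 63%.

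The gain over chi-squared is therefore about 10 to 20 points, depending on the assumed distribution.

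**5. The other quoted pair, 33.3% vs 93.5%.** On the normal scale d = 1.95, and both tests have about 100% power. Nothing is lost.

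**6. Can 35% vs 51% be patient proportions?** The background section gives the source trial 40 patients. A rounded 35% needs an arm of at least 17 (6/17) and a rounded 51% an arm of at least 35 (18/35), and 17 + 35 = 52. Allowing truncation as well as rounding, the smallest arms are 14 (5/14) and 27 (14/27), and 14 + 27 = 41. No split of 40 or fewer patients gives the pair. By contrast, 33.3% vs 93.5% among 61 patients fits 10/30 and 29/31.

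**7. Does the window match?** The 35% vs 51% covers 24 hours after DKA resolution. The III.D outcome covers 24 hours from glargine, which the intervention group receives within 4 hours of starting the infusion. The event rate in that window is not given.

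**The case against.** The strongest case against is that this is largely preference. Hyperglycemia is one of six secondary outcomes, no power is claimed for it, and neither specific aim mentions it. An incidence above 180 mg/dL matches the upper end of the stated post-resolution target, is easy for clinicians to read and resembles the rebound outcome in the cited work. Most of this stands: it limits the weight of the point and is a reason to keep the incidence in the report. It does not explain why a per-patient mean or median that III.B already derives is compared only after banding.

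A reader might infer that the plan loses 20 points of power at its own quoted rates. The documents do not support that. Twenty points is the top of the range under one distribution. It rests on a pair of rates that cannot be patient proportions as quoted and that comes from another window, and the second quoted pair shows no loss.

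A reader might also conclude that peak glucose in the 24 hours from glargine should be tested instead, because that is the quantity the >180 rule cuts. This would be unsound. The DKA definition includes glucose of at least 250 mg/dL, so an early peak would largely reflect presenting glucose. Controls by definition had no basal insulin before anion gap closure, so a glargine-anchored window starts later in their course, after treatment has lowered glucose. The comparison would tend to count against the intervention, and a more sensitive scale would sharpen that bias.

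Finally, it would be wrong to say the data sheet records only yes or no, since it also has time and severity fields.

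**Conclusion.** The structural point holds: every planned hyperglycemia comparison is either a >180 mg/dL cut or a banding of the per-patient mean or median, and none is made on the glucose scale. That discards information without a stated reason.

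The size of the loss cannot be fixed from the documents. The illustration of about 53% power for the yes/no test against about 63 to 74% uncut assumes 80 per group, patient-level rates of 35% and 51%, and one cut on an equal-spread scale. The second assumption fails on the background section's own trial size, so these figures show what cutting can cost, not what it costs here. They also describe the variable cut at 180 and do not transfer directly to a per-patient mean.

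This is a modest, inexpensive improvement to a secondary outcome. It gives no ground for saying that the trial is too small or that the primary analysis is affected. Nor does analysing glucose uncut remove any bias from comparing prospective patients with historical controls.

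**What to change.** In III.B, III.D and V, name per-patient mean glucose (or median, under the plan's normality rule) as the tested hyperglycemia measure. Compare it uncut by the existing t-test/Mann-Whitney rule, and report the difference in mg/dL with a 95% CI. Define the window the same way in both groups; the 24 hours after the insulin infusion stops, already on the data sheet, is one candidate. Do not use peak glucose from the time of glargine.

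Record the numeric glucose values in the data sheet. Keep the incidence above 180 mg/dL and the III.B bands as descriptive results.

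The cost is a few sentences and one extra derived field, built from readings that III.A and VI say are taken routinely; for controls this assumes the readings can be retrieved from the chart. A difference in mg/dL is less familiar to clinicians than an incidence, which is why the incidence stays. No extra patients or glucose checks are needed, and clinical management does not change.
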